4.3 Exclusion Criteria

- Any other serious medical condition which in the Investigator's opinion would preclude safe participation in the study.
- Subjects, in the opinion of the Investigator, who are unsuitable to participate in the study.

- Known history of difficulty swallowing, malabsorption or other conditions that may reduce absorption of the product.
- Patients with history of TIA or stroke within the past 12 months are excluded.
- Subjects with significant cardiac dysfunction as defined by the following:
 - Myocardial infarction within 6 months prior to study registration;
 - Unstable angina pectoris;
 - New York Heart Association (NYHA) Class III/IV congestive heart failure;
 - Uncontrolled hypertensive urgency or emergency;
 - Cardiac conduction abnormalities (e.g., symptomatic or sustained atrial or ventricular arrhythmias, second- or third-degree atrioventricular block, complete bundle branch blocks) that, in the investigator's medical judgement, makes them unsuitable for clinical trial.
 - Moderate or severe valvular heart disease, documented by cardiac doppler echocardiogram (Echo) or cardiac MRI (CMR), that in the investigator's medical judgement, makes them unsuitable for clinical trial.
- Pregnancy or breast-feeding for the entire duration of study participation or in the 30 days following the last dose of study drug. Due to the potentially teratogenic effects of TGF β inhibition during development, pregnant and nursing subjects may not be enrolled and pregnancy must be avoided.
- **Note:** Women of child-bearing potential—defined as sexually active woman who has not undergone hysterectomy and who has had menses any time within the preceding 24 months—must have a negative serum or urine pregnancy test 7 days prior to registration.
- Female subjects who are breastfeeding, or intend to breastfeed, during the study or in the 30 days following the last dose of study drug are excluded.
- Women and men of childbearing potential must either commit to continued abstinence from heterosexual intercourse or commit to simultaneous use of two acceptable methods of birth control—one highly effective method (e.g., IUD, tubal ligation or vasectomy) of patient or partner, and one additional effective method (e.g., latex condom, diaphragm or cervical cap) from the time of screening through 90 days following the last dose of study drug. Use of oral contraceptives is not allowed.
- Current or planned use of any of the following classes of drugs during the study period:
 - Drugs which are exclusively or primarily eliminated by cytochrome P-450 isozyme 3A4 (CYP)3A4 or by UDP glucuronyltransferase 1A1 (UGT)1A1.
 - Drugs which are substrates for the drug transporter multidrug resistance protein 1 (MDR1) and have a narrow therapeutic window; or which are strong inhibitors of drug transporter MDR1.
 - Any major surgeries within 28 days of study enrollment.

4.4 Lifestyle Considerations

- Not applicable

4.5 Screen Failures

Screen failures are defined as participants who consent to participate in the clinical trial but are not subsequently assigned to the study intervention or entered in the study. Individuals who do not

meet the criteria for participation in this trial (screen failure) because of a modifiable factor may potentially be rescreened. Rescreened participants should be assigned the same participant number as for the initial screening.

4.6 Strategies for Recruitment and Retention

- The study will be listed or otherwise included on government (clinicaltrials.gov), philanthropic (MPN-RF, CR&T) and institutional (Richard T Silver MPN Center) websites, Facebook and Twitter accounts (as applicable).

5. Registration Procedures

5.1 Subject Registration

Subjects will be registered within the WRG-CT as per the standard operating procedure for this process.

6. Study Procedures

6.1 Schedule of Assessments

Table 1a. Tier 1 schedule of trial events 6.1.1

Tier 1 Schedule of Assessments	Screening	Treatment Tier 1															
		Cycle 1				Cycle 2				Cycle 3				Cycle 4			
Pre-study D-28 to -1		Wk1 ^a	Wk2 ^a	Wk3 ^a	Wk4 ^a	Wk5 ^a	Wk6 ^a	Wk7 ^a	Wk8 ^a	Wk9 ^a	Wk10 ^a	Wk11 ^a	Wk12 ^a	Wk13 ^a	Wk14 ^a	Wk15 ^a	Wk16 ^a
Informed Consent Form	X																
Inclusion/Exclusion Criteria	X															X	
Enrollment	X																
Demographics	X																
Diagnosis	X																
Medical History ^b	X	X	X	X	X	X	X	X	X	X	X	X	X	X	X	X	
Vital Signs	X	X	X	X	X	X	X	X	X	X	X	X	X	X	X	X	
Physical Examination ^c	X	X	X	X	X	X	X	X	X	X	X	X	X	X	X	X	
Medications	X	X	X	X	X	X	X	X	X	X	X	X	X	X	X	X	
ECOG	X	X	X	X	X	X	X	X	X	X	X	X	X	X	X	X	
Toxicity / AE assessment		X	X	X	X	X	X	X	X	X	X	X	X	X	X	X	
Con Med assessment		X	X	X	X	X	X	X	X	X	X	X	X	X	X	X	
Blood tests ^d	X	X	X	X	X	X	X	X	X	X	X	X	X	X	X	X	
Troponin, BNP, CK-MB	X													X			
EPO level	X					X				X				X			
Pregnancy test	X																
Electrocardiogram (EKG) ^e	X	e	e	e	e	e	e	e	e	e	e	e	e	e	e	e	

End of Tier 1 – Patients meeting composite response and toxicity endpoint may continue to accrue

Echocardiography with Doppler ^f	X																								
Bone Marrow Aspirate and Biopsy	X																								X
Ultrasound (left upper quadrant)	X																								X
Research blood	X	X						X								X					X			X	
Research Bone Marrow	X																								X
Treatment Administration Form and Compliance assessment		X	X	X	X	X	X	X	X	X	X	X	X	X	X	X	X	X	X	X	X	X	X	X	
MPN-SAF form		X	X	X	X	X	X	X	X	X	X	X	X	X	X	X	X	X	X	X	X	X	X	X	
Record HgB level and HgB change ^g		X	X	X	X	X	X	X	X	X	X	X	X	X	X	X	X	X	X	X	X	X	X	X	
Record RBC transfusion history		X ^h	X	X	X	X	X	X	X	X	X	X	X	X	X	X	X	X	X	X	X	X	X	X	
Composite response and toxicity endpoint assessment																									X

a. Visits are weekly if there is a dose change (escalated or reduced or held for toxicity). Visits are biweekly if dose is maintained. Visits are extended to every 4 weeks (once per cycle) as long as dose is maintained for 4 weeks.

b. Must record baseline comorbidities, pre-existing symptoms

c. Spleen size should be recorded

d. Blood tests are: CBC, CMP, UA, Phosphorous, LDH

e. Electrocardiogram required at screening. Only required at subsequent visits in the event of a dose increase.

f. Echocardiogram or Cardiac MRI will be done once every 2 cycles (8 weeks or 56 days)

g. Baseline HgB is defined as median HgB within 28 days of Cycle 1, Day 1

h. Include erythrocyte transfusion history 8 weeks prior to screening

Tier 2 Schedule of Assessments	Screening	Treatment Tier 2																						End of Tier2 p patients meeting composite response and toxicity endpoints may continue vactosertib		
		Cycle 1			Cycle 2			Cycle 3			Cycle 4			Cycle 5			Cycle 6									
	Pre-study D-28 to -1	Wk1 ^a	Wk2 ^a	Wk3 ^a	Wk4 ^a	Wk5 ^a	Wk6 ^a	Wk7 ^a	Wk8 ^a	Wk9 ^a	Wk10 ^a	Wk11 ^a	Wk12 ^a	Wk13 ^a	Wk14 ^a	Wk15 ^a	Wk16 ^a	Wk17 ^a	Wk18 ^a	Wk19 ^a	Wk20 ^a	Wk21 ^a	Wk22 ^a	Wk23 ^a	Wk24	
Informed Consent Form	X																									
Inclusion/Exclusion Criteria	X																									
Enrollment	X																									
Demographics	X																									
Diagnosis	X																									
Medical History ^b	X	X	X	X	X	X	X	X	X	X	X	X	X	X	X	X	X	X	X	X	X	X	X	X	X	
Vital Signs	X	X	X	X	X	X	X	X	X	X	X	X	X	X	X	X	X	X	X	X	X	X	X	X	X	
Physical Examination ^c	X	X	X	X	X	X	X	X	X	X	X	X	X	X	X	X	X	X	X	X	X	X	X	X	X	
Medications	X	X	X	X	X	X	X	X	X	X	X	X	X	X	X	X	X	X	X	X	X	X	X	X	X	
ECOG	X	X	X	X	X	X	X	X	X	X	X	X	X	X	X	X	X	X	X	X	X	X	X	X	X	
Toxicity / AE assessment	X	X	X	X	X	X	X	X	X	X	X	X	X	X	X	X	X	X	X	X	X	X	X	X	X	
Con Med assessment	X	X	X	X	X	X	X	X	X	X	X	X	X	X	X	X	X	X	X	X	X	X	X	X	X	
Blood tests ^d	X	X	X	X	X	X	X	X	X	X	X	X	X	X	X	X	X	X	X	X	X	X	X	X	X	
Troponin, BNP, CK-MB	X																									X
EPO level	X					X			X										X						X	
Pregnancy test	X																									
Electrocardiogram (EKG) ^e	X	e	e	e	e	e	e	e	e	e	e	e	e	e	e	e	e	e	e	e	e	e	e	e	e	
Echocardiography with Doppler ^f	X																									X
Bone Marrow Aspirate and Biopsy	X																									X
Ultrasound (left upper quadrant)	X																									X
Research blood	X	X				X			X										X						X	
Research Bone Marrow	X																									X
Treatment Administration Form and Compliance assessment		X	X	X	X	X	X	X	X	X	X	X	X	X	X	X	X	X	X	X	X	X	X	X	X	
MPN-SAF form		X	X	X	X	X	X	X	X	X	X	X	X	X	X	X	X	X	X	X	X	X	X	X	X	

*Patients who have completed Tier 1 would not require repeat assessments if done within 28 days of Tier 2 enrollment

- a. Visits are weekly if there is a dose change (escalated or reduced or held for toxicity). Visits are biweekly if dose is maintained. Visits are extended to every 4 weeks (once per cycle) as long as dose is maintained for 4 weeks.
- b. Must record baseline comorbidities, pre-existing symptoms
- c. Spleen size should be recorded
- d. Blood tests are: CBC, CMP, UA, Phosphorous, LDH
- e. Electrocardiogram required at screening. Only required at subsequent visits in the event of a dose increase.
- f. Echocardiogram or Cardiac MRI will be done once every 2 cycles (8 weeks or 56 days)
- g. Baseline HgB is defined as median HgB within 28 days of Cycle 1, Day 1
- h. Include erythrocyte transfusion history 8 weeks prior to screening

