- To identify common toxicities of vactosertib in patients with Ph-neg MPNs.

Exploratory Objectives:

To assess the stem cell directed effect of vactosertib by quantifying the VAF of MPN driver mutations in stem, progenitor and mature cell populations isolated from PB or BM samples before and after treatment with vactosertib.

Endpoints:

Primary Endpoints: (Safety and Efficacy)

- Tier 1 (Safety endpoints):
 - Define the safest, minimally effective starting DL for Tier 2 ([section 5.3.5.1](#)).
 - Identify DLTs and, possibly the MTD of vactosertib in patients with MPN
- Tier 2 Efficacy endpoints ([section 9.1](#)):
 - Erythropoietic response as defined by the IWG-MRT criteria
 - Clinical response in symptoms as defined by IWG criteria.
 - Splenic response as defined by IWG criteria.^{2,3}
- Tier 2 Safety endpoints: Identify DLT and, possibly MTD

Secondary Endpoints:

- Histologic response defined by any reduction in grade of bone marrow fibrosis by histopathologic assessment at 16 weeks.
- Molecular response defined by a decrease in VAF of MPN-driver mutations (eg. JAK2, CALR, and MPL allelic ratio) in blood and/or bone marrow cells.
- Pharmacodynamic Response defined as any of the following:
 - Reduced immunohistochemical staining for SMAD2/3 phosphorylation in bone marrow biopsy sections (*See Figure 1*).
 - Reduced mean fluorescence intensity (MFI) of SMAD2/3 phosphorylation staining in peripheral blood and/or bone marrow HSPCs or mature progeny as assessed by flow cytometry (*See Figure 2*).
- The incidence of hematologic toxicities, infections, disease progression, thrombosis events, and the probability of overall and progression free survival, will be monitored.

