7.7.2 Dosing Delays/Dose Modifications for vactosertib

Clinical Parameter	Escalate to Next Dose Level	Maintain Current Dose Level	Hold Dose	Restart After Dose Hold
Erythropoietic Response	Inadequate	Adequate		
Hemoglobin (HGB) absolute value, change in HGB from baseline*, and Erythrocyte transfusion	HGB ≤10 g/dL AND ≤2 g/dL increase from baseline HGB OR any Erythrocyte transfusion	HGB >10 g/dL OR >2g/dL increase from baseline HGB AND No Erythrocyte transfusion	HGB >12 g/dL	HGB<12 g/dL
Current Toxicity (CTCAE v5)	≤Grade 2	≤Grade 2 OR >Grade 2 not requiring change in treatment	>Grade 2 Requiring Change in Treatment	<Grade 2 and Requiring No New Change in Treatment
Dose hold Toxicity during Cycle	Dose Hold Not Required During Cycle	Dose Hold Not Required During Cycle		
Current Dose Dose Levels: (DL0) 50 mg daily; (DL1) 50 mg bid; (DL2) 100 mg bid; (DL3) 150 mg bid; (DL4) 200 mg bid.	< Highest Dose Level	≤ Highest Dose Level		Most Recent Dose >(DL0)
Dosing schedule, 5 days on, 2 days off				
Rule	All True	All True	Any True	All True
Next Study Visit [†]	7±2 days	1 st Maintain [§] 14±3 days 2 nd or greater Maintain D1 of next cycle	7±2 days	7±2 days

Table 3: Intrapatient Dose Adjustment Rules.

The parameters shown are used to adjust the vactosertib dose on a continuing basis. The dose is escalated to the next level if ALL criteria for escalation are met. The decision to Hold vactosertib is made if ANY hold criteria is met at any point during the cycle. Otherwise the dose level is maintained. The criteria to Escalate, Maintain or Hold a dose are non-overlapping. Dose decrements by one level will follow any HOLD. * Baseline HGB is defined as the median HGB in the 4 weeks prior to D1 of protocol treatment. † Subject will maintain a diary of adverse events between study visits. [§]Visits are weekly if there is a dose change (Escalate, Hold or Restart). Visits are bi-weekly if the decision is to Maintain the current dose. Visits are extended to every 4 weeks (D1 of each new cycle) after the second or greater, consecutive Maintain decision.

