12.6 Reporting and Exclusions

12.6.1 Evaluation of Toxicity

All patients will be evaluable for toxicity from the time of their first treatment with vactosertib. Consultation with the Biostatistics Office will allow for completion of this section.

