Table 11: Adverse drug reaction (≥3%) from vactosertib monotherapy

AE Terms	MP-001 (n=35), n (%)	MP-VAC-105 (n=16), n (%)	MP-MDS-01 (n=9), n (%)	Total (n=60), n (%)
Headache	5 (15)	5 (32)	1 (12)	11 (19)
Fatigue	10 (29)	0 (0)	1 (12)	11 (19)
Nausea	9 (26)	1 (7)	0 (0)	10 (17)
Diarrhoea	5 (15)	1 (7)	1 (12)	7 (12)
Decreased appetite	6 (18)	0 (0)	0 (0)	6 (10)

Vomiting	5 (15)	0 (0)	0 (0)	5 (9)
Hypophosphataemia	3 (9)	0 (0)	1 (12)	4 (7)
Constipation	4 (12)	0 (0)	0 (0)	4 (7)
Dermatitis acneiform	2 (6)	0 (0)	1 (12)	3 (5)
Aspartate aminotransferase increased	3 (9)	0 (0)	0 (0)	3 (5)
Pruritus	3 (9)	0 (0)	0 (0)	3 (5)
Abdominal pain	2 (6)	0 (0)	0 (0)	2 (4)
Alanine aminotransferase increased	2 (6)	0 (0)	0 (0)	2 (4)
Amylase increased	2 (6)	0 (0)	0 (0)	2 (4)
Anaemia	2 (6)	0 (0)	0 (0)	2 (4)
Blood alkaline phosphatase increased	2 (6)	0 (0)	0 (0)	2 (4)
Dysgeusia	2 (6)	0 (0)	0 (0)	2 (4)
Dyspepsia	2 (6)	0 (0)	0 (0)	2 (4)
Lipase increased	2 (6)	0 (0)	0 (0)	2 (4)
Muscular weakness	2 (6)	0 (0)	0 (0)	2 (4)
Pyrexia	2 (6)	0 (0)	0 (0)	2 (4)
Rash maculo-papular	2 (6)	0 (0)	0 (0)	2 (4)

- Vactosertib may increase immunologic toxicities of when administered in combination with anti-cancer PD1/PD-L1 pathway inhibitors.

Dose Limiting Toxicity.

- Dose limiting toxicity is defined as any of the following: Any occurrence of death as result of adverse event regardless of attribution;
- Any non-hematologic grade ≥ 3 toxicity (CTCAEv5 criteria), except for nausea, vomiting or diarrhea lasting 3 days or less;
- Any grade 4 neutropenia (CTCAEv5 criteria) of any duration;
- Any grade ≥ 3 neutropenia that has not recovered to grade ≤ 2 within 7 days of onset;
- Any grade ≥ 3 febrile neutropenia (temperature \geq);
- Any grade ≥ 3 thrombocytopenia associated with clinically significant bleeding; or requiring platelet transfusion.

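### Raw DLT counts per dose level carry no exposure denominator, although a weekly escalator spends one week on each of DL1 to DL3 and nine weeks on DL4

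*Combined protocol and SAP*

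**What the plan says.** Section 6.1, footnote a, ties visit spacing to the dose decision: "Visits are weekly if there is a dose change (escalated or reduced or held for toxicity"), then "Visits are biweekly if dose is maintained", and then "Visits are extended to every 4 weeks (once per cycle) as long as dose is maintained for 4 weeks". Table 3 (Section 7.7.2) repeats this: "Visits are extended to every 4 weeks (D1 of each new cycle) after the second or greater, consecutive Maintain decision". The schedule places the blood tests at these visits: "Blood tests are: CBC, CMP, UA, Phosphorous, LDH".

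DLT counts by dose level are used in three places:
- **Suspension of a level.** Section 8.1.1 suspends accrual to a level and those above it when more than two patients have a DLT there. Section 12.5 sets the trigger at more than three.
- **Tier 2 starting dose and Safe Minimum Dose** (Sections 6.3.6.3 and 12.6.3). Both look for the lowest level with no DLT in Tier 1, combined with a clinical-benefit condition. Neither states a minimum exposure.
- **The Tier 1 safety endpoint** in the Protocol Summary: "Identify DLTs and, possibly the MTD of vactosertib in patients with MPN".

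The study-wide stopping rules in Sections 8.1.1 and 8.1.2 pool DLTs over all doses within 12 weeks. Section 12.6.1 says "All patients will be evaluable for toxicity from the time of their first treatment with vactosertib" and adds that it is to be completed with the Biostatistics Office. It gives no person-time denominator and no rule for attributing a DLT to a level.

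The DLT definition (Section 13.1.1) includes "Any grade 4 neutropenia (CTCAEv5 criteria) of any duration" and grade 3 or higher neutropenia that has not recovered to grade 2 or below within 7 days of onset.

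**The concern.** A count of DLTs at a level depends on three things: the hazard at that level, the time patients spend there, and how often anyone looks. The escalation rule makes the second very unequal between levels, and the visit rule makes the third depend on the last dose decision. A raw count mixes all three.

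Zero DLTs at DL1 after one week per patient is weak evidence of safety, while a few at DL4 over nine weeks may reflect no higher hazard. If the counts are taken at face value, a level can qualify as DLT-free, or be suspended, mainly because of how long patients were on it.

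**Working it through.** **Dose and visit path (Table 3).** For a patient with inadequate response and no hold:

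| Level | Days | Length | Visits |
|---|---|---|---|
| DL1 | 0–7 | 7 | 7 |
| DL2 | 7–14 | 7 | 14 |
| DL3 | 14–21 | 7 | 21 |
| DL4 | 21–84 | 63 | 28, 42, 56, 84 |

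Twelve such patients give 12 × 1 = 12 patient-weeks at each of DL1 to DL3 and 12 × 9 = 108 at DL4.

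**Exposure alone.** Assume a constant hazard that is the same at every dose, with a 12-week DLT probability of 20%, and ignore time lost after a DLT.
- Weekly hazard: h = −ln(0.80)/12 = 0.0186.
- P(no DLT at DL1) = exp(−12 × 0.0186) = 80%.
- P(no DLT at DL4) = exp(−108 × 0.0186) = 13%.

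The same assumption carries through to the suspension trigger of more than two patients in Section 8.1.1. The per-patient probability is 1 − exp(−0.0186) = 1.8% at DL1 and 1 − exp(−9 × 0.0186) = 15.4% at DL4. The binomial probability of 3 or more of 12 is then 0.1% and 28%. No dose effect is involved.

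**What zero events would show.** The exact Poisson upper limit (two-sided 95%) for zero events is −ln(0.025) divided by exposure. That is 3.69/12 = 0.31 per patient-week at DL1 and 3.69/108 = 0.034 at DL4. The DL1 limit is about 17 times the assumed hazard (0.307/0.0186).

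**Secondary point: detection.** Assume a silent laboratory episode of d days with uniform onset, seen only if a scheduled visit falls within it. Detection is Σ min(d, T) / Σ T over the visit intervals T.
- DL4 (intervals 7, 14, 14, 28): for d = 7, 28/63 = 44%; for d = 14, 49/63 = 78%.
- Maintained at DL1, after day 7 (visits 21, 28, 56, 84; intervals 14, 7, 28, 28): for d = 7, 28/77 = 36%; for d = 14, 49/77 = 64%.
- Weekly escalator over all 84 days: for d = 7, 49/84 = 58%; for d = 14, 70/84 = 83%.
- For d = 28 or longer, or for a clinically apparent event, detection is 100%.

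**Effect on the pooled stopping rules.** The Section 8.1 tables come first. The Tier 1 table gives 12/35/56/73/91% at true rates of 5/10/15/20/30%. The written rule (3 or more of 12) gives 2.0/11.1/26.4/44.2/74.7%; a trigger of 2 or more gives 11.8/34.1/55.7/72.5/91.5%. The Tier 2 table (3.1/31/67/89/99%) likewise fits 5 or more of 37 and not the written 6 or more, which gives 77.8% at a 20% rate. That mismatch is a separate matter. The figures below use the written rules and leave out the grade 5 trigger, for which no rate is given.

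At a true rate of 20%, let q be the share of DLTs that are silent 7-day laboratory events. The ascertained rate is 0.20 × [1 − q(1 − 49/84)].

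| q | P(3 or more of 12) | P(6 or more of 37) |
|---|---|---|
| 0 | 44% | 78% |
| 22% | 38% | 69% |
| 25% | 37% | 67% |
| 50% | 29% | 54% |
| 100% | 16% | 26% |

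The documents do not give q. The 22% row is a rough guide from Table 7 (grade 3 or 4 events, vactosertib monotherapy). Of 38 listed event counts, 36 remain without anaemia, and 8 of these are laboratory terms (hyponatraemia 2; acidosis, ALT, AST, bilirubin, hypokalaemia and hypophosphataemia 1 each); 8/36 = 22%. With 14-day episodes that row becomes 42% and 74%.

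**Neutropenia recovery.** Table 3 allows Maintain with a toxicity above grade 2 that needs no change in treatment. The next scheduled visit is then 14 days away, or Day 1 of the next cycle (up to 28 days). Scheduled blood counts at that spacing cannot establish whether neutropenia recovered within 7 days of onset.

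**The case against.** A reader might infer that DLTs at the highest dose are the least likely to be seen. The documents do not support that. Thinning follows Maintain at any level, and detection of a 7-day episode is lower in a patient maintained at DL1 (36%) than at DL4 (44%). With 63 of 84 days at DL4, the raw count is expected to be highest there.

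A reader might also infer that the stopping rules are badly weakened. The large losses need 50% to 100% of DLTs to be silent laboratory events lasting 7 days. Table 7 lists no neutropenia or thrombocytopenia, though it comes from other populations and Section 13.1.1 says there are no data in advanced MPNs. Most DLT categories are clinically apparent, a diary covers the time between visits (Section 6.3.4.3), and hold criteria apply at any time in the cycle. Standard-of-care blood draws would recover some missed events.

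The plan makes no formal comparison between levels. The study-wide rules pool doses, the MTD is only a possible output, and the starting-dose rule takes the lowest qualifying level, so a DLT missed at DL4 would seldom change it.

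All of this stands, and it limits the detection point. It does not answer the exposure point: the suspension and starting-dose rules act on per-level counts, and a low level can qualify after one week per patient.

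**Conclusion.** The point holds as one about unequal exposure. For patients who escalate weekly, time in the 12-week window differs ninefold between DL4 and each lower level, and the per-level rules ignore it. The 80% and 13% rest on three assumptions: a 20% 12-week rate, a constant dose-independent hazard, and all 12 patients escalating weekly. Patients who respond early would shift exposure towards lower levels.

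The ascertainment point is secondary. It concerns brief silent laboratory events at any maintained level, and it lowers the sensitivity of the pooled rules modestly at the Table 7 share (78% to 69% or 74% for 37 patients). Its true size depends on episode duration and laboratory-only share, neither of which is given. This is a cheap improvement to reporting and interpretation, not a flaw that invalidates the design.

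**What to change.** Complete Section 12.6.1 as follows:
1. For each dose level, report patients treated, patient-weeks, raw DLT count, and DLTs per patient-week with an exact Poisson interval. Interpret any per-level safety or MTD statement on that basis.
2. State the level to which a DLT is attributed when it appears after a dose change.
3. Score laboratory DLTs from every available CBC and CMP, including standard-of-care draws between visits.
4. Show DLTs in the first 7 days at each level only as a supplementary table. As the basis for an MTD statement it would discard about eight of the nine DL4 weeks and all delayed toxicity.

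Two pairs of passages must be reconciled: the 7-day neutropenia-recovery criterion (Section 13.1.1) with the 14- to 28-day visit spacing after Maintain (Table 3), and the same-level DLT triggers in Sections 8.1.1 and 12.5.

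The cost is SAP wording, one table, and abstraction of whatever laboratory results exist outside study visits. The downside is that estimates at DL1 to DL3 will show wide intervals, which is an honest account of one week per patient.

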Study Description:	
This is a two-tiered single arm Phase 2 trial of vactosertib (TEW-7197) for the treatment of anemia in Ph-neg MPNs. Both tiers use a rule-based, accelerated dose escalation scheme to efficiently assess the potential of vactosertib to safely and effectively treat anemic patients with Ph-neg MPNs. The first tier of this trial (Tier 1) is an intra-patient dose finding study in 12 patients that uses a low starting dose of vactosertib for all patients. Treatment dose is escalated according to prospectively-defined rules, and a toxicity and treatment effect algorithm (Table 3 in section 7) during the period of 16 weeks (4 treatment cycles). If pre-established efficacy and safety endpoints are met (section 12.1), then Tier 1 of the study will be followed by a Tier 2 expansion study with an additional 25 patients for a period of 24 weeks (6 treatment cycles).
 
Vactosertib will be administered in combination with stable dose of current therapy. Prior to enrollment patients must be on a stable dose of their current therapy for 3 months prior to entering the study. For patients not receiving cytoreductive therapies (e.g., interferon, hydroxyurea, DNA hypomethylating agents or other cytotoxic chemotherapy) must be off their most recent for a period of at least 14 days or 5 half-lives, whichever is longer. Supportive care measures including packed red blood cell (PRBC) transfusions for HGB <7g/dL, or symptomatic anemia, will be permitted. Administration of erythropoiesis stimulating agents (ESAs), however, will not be permitted on the trial (patients recruited would have serum EPO >125 U/L above which the benefit of ESAs is not supported)¹.

Sample Size:	Total = 37 subjects (N = 12 for Tier 1, N = 25 for Tier 2)
Enrollment:	This study will enroll 37 subjects and screen up to 100 subjects.
Study Population:	Patients of age \geq 18 with anemia due to Ph-neg MPNs
Enrollment Period:	72 months

Study Design:

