12.1 Study Design/Endpoints

12.1.1. Optimal Two-Stage Design, and Criteria to Proceed to Tier 2:

A Simon Two-stage Optimum Design was used to minimize the number of subjects exposed to vactosertib if it is found to be an unsuitable agent for the treatment of anemic patients with Ph-neg MPNs. Further development of vactosertib would be warranted if $\geq 20\%$ of subjects met *Criteria for Clinical Benefit* ([section 10.1](#)) without dose-limiting toxicity (see *Definition of Dose Limiting Toxicity* section). The study will be terminated early if fewer than 1 subject treated in the first tier (up to 12 subjects) meet these criteria. Using these criteria, there is less than a 10% chance of inappropriately accepting (α , type 1 error) vactosertib if it is not truly useful. Conversely, there is less than a 10% chance of inappropriately rejecting (β , type 2 error) vactosertib if it is actually a useful drug for anemic patients with Ph-neg MPNs.

Table 4: Optimal Two Stage Design

Response Probability Indicating Unacceptably Low vactosertib Activity	0.05
Response Probability Indicating Substantial vactosertib Activity	0.20
Probability of Accepting Poor Drug	0.1
Probability of Rejecting Good Drug	0.1
Number of Tier 1 Subjects	12
Number of Tier 1 Responders to Advance to Tier 2	≥ 1
Maximal Number of Subjects	37
Number of Tier 2 Responders to Advance Development	≥ 4

The Simon Two-stage Optimum Design is expected to minimize the number of subjects exposed to vactosertib if it is found to be an unsuitable agent for the treatment of anemic patients with Ph-neg MPNs (see *Criteria for Decision to Proceed to Tier 2* section). If 1 or more subjects meets the *Composite Response & Toxicity Endpoint* ([Table 5](#)) then the study will proceed to Tier 2 and another 25 subjects will be enrolled. After completion of Tier 2, if four or more subjects meet the *Composite Response & Toxicity Endpoint* then vactosertib

will have shown preliminary efficacy and feasibility to justify further evaluation as an agent to treat anemic patients with Ph-Neg MPNs.

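### Table 4 labels the final threshold as Tier 2 responders, which read as printed gives 71.3% power; the stated error rates need 4 of 37 distinct subjects, and a Tier 2 footnote on Tier 1 completers blurs who counts

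*Combined protocol and SAP*

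**What the plan says.** Section 12.1.1 describes a Simon optimal two-stage design with response rates 0.05 ("Response Probability Indicating Unacceptably Low vactosertib Activity") and 0.20 ("Response Probability Indicating Substantial vactosertib Activity"). It states that "there is less than a 10% chance of inappropriately accepting" the drug if it is not useful, and that "there is less than a 10% chance of inappropriately rejecting" it if it is. Table 4 lists 12 Tier 1 subjects, at least 1 Tier 1 responder to go on, a maximum of 37 subjects, and a last row reading "Number of Tier 2 Responders to Advance Development", at least 4. The text of 12.1.1 and of Section 15 asks for four or more subjects meeting the composite endpoint once Tier 2 is complete. Neither says from which subjects the four are drawn.

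On who fills Tier 2, the Protocol Summary describes a "Tier 2 expansion study with an additional 25 patients". Sections 6.3.6, 12.1.1 and 15 likewise speak of further subjects, Section 12.2 gives 37 as 12 plus 25, and Section 8.1.1 gives 37 accrued across the two tiers.

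Two entries in Section 6.1 sit uneasily with this. The footnote to the Tier 2 schedule says "Patients who have completed Tier 1 would not require repeat assessments if done within 28 days of Tier 2 enrollment". The end-of-tier note on the Tier 1 schedule says "Patients meeting composite response and toxicity endpoint may continue to accrue", where the matching Tier 2 note speaks of continuing vactosertib. Section 6.3.7 offers completers of either tier continued drug as ongoing treatment and does not call this Tier 2 enrolment.

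**The concern.** The last row of Table 4 is the trial's efficacy decision rule. The row for Tier 1 responders plainly means responders among the 12 Tier 1 subjects, so the parallel wording for Tier 2 points to responders among the 25. A two-stage design of this kind gets its power from carrying stage 1 responders into the final count. Dropping them makes the threshold much harder to reach.

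The footnote raises a second doubt about the same count. It has a function only if someone who completed Tier 1 can enrol in Tier 2. The design calculation needs 37 different people, each contributing one result. If Tier 1 completers can occupy Tier 2 places, the plan should say how they are counted, and it does not.

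The trial is open label with a single arm. An unsettled counting rule could be resolved after responses are known, when a result of, say, 1 responder in Tier 1 and 3 in Tier 2 would pass on one reading and fail on the other.

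**Working it through.** **Inputs** (Table 4 and Section 12.2): p0 = 0.05, p1 = 0.20, n1 = 12, n2 = 25, total 37; continue if X1 ≥ 1; final threshold 4. X1 ~ Bin(12, p) is the number of Tier 1 responders and X2 ~ Bin(25, p) the number in Tier 2.

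**1. The plan's own figures: cumulative count over 37 distinct subjects**

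P(accept) = Σ over x ≥ 1 of P(X1 = x) · P(X2 ≥ 4 − x)

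| x | P(X1 = x), p = 0.05 | P(X2 ≥ 4 − x) | Product | P(X1 = x), p = 0.20 | P(X2 ≥ 4 − x) | Product |
|---|---|---|---|---|---|---|
| 1 | 0.3413 | 0.1271 | 0.0434 | 0.2062 | 0.9018 | 0.1859 |
| 2 | 0.0988 | 0.3576 | 0.0353 | 0.2835 | 0.9726 | 0.2757 |
| 3 | 0.0173 | 0.7226 | 0.0125 | 0.2362 | 0.9962 | 0.2353 |
| ≥ 4 | 0.0022 | 1 | 0.0022 | 0.2054 | 1 | 0.2054 |
| Total (from unrounded terms) | | | **0.0935** | | | **0.9024** |

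Type I error is 9.3% and type II error is 9.8%, both below 10%. A search over designs with total size 15 to 45 at 10%/10% returns exactly this one as the Simon optimum (stop at 0 of 12, reject at 3 or fewer of 37; expected size 23.5 under p0). So this is the rule that Table 4 was built on.

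**2. Table 4 label as printed: at least 4 of the 25 Tier 2 subjects, after the Tier 1 gate**

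P(accept) = P(X1 ≥ 1) · P(X2 ≥ 4)

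- p = 0.05: 0.4596 × 0.0341 = 0.0157
- p = 0.20: 0.9313 × 0.7660 = 0.7134

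Type I error is 1.6%, power 71.3%, type II error 28.7%.

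**3. Footnote: Tier 1 subjects take some of the 25 places, each person counted once**

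The documents give no re-enrolment rate, so the rates here are assumptions. Suppose each Tier 1 responder independently re-enrols with probability q, k of the x do so, and only 25 − k places go to new subjects. Acceptance needs x + Bin(25 − k, p) ≥ 4 with x ≥ 1.

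| q | Type I error | Power |
|---|---|---|
| 25% | 9.1% | 90.1% |
| 50% | 8.9% | 89.9% |
| 100% | 8.5% | 89.5% |

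If instead a fixed number m of Tier 1 subjects re-enrol regardless of response, m = 3, 6 or 12 gives power 88.4%, 85.6% or 74.9%, with type I error 7.6%, 6.0% or 3.2%.

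**4. Hypothetical only: re-enrolled responders counted in both tiers**

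Acceptance needs x + k + Bin(25 − k, p) ≥ 4 with x ≥ 1. For q = 25%, 50% and 100%, type I error is 13.1%, 16.7% and 23.4%.

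**The case against.** The best defence is that the design is sound and its meaning recoverable. Table 4 is titled as a two-stage design, places the threshold directly below a maximum of 37 subjects, and states errors of 0.1 and 0.1; only the cumulative count fits all three. The text of 12.1.1 and Section 15 counts subjects without confining them to Tier 2, and one person is one subject. Sections 1, 6.3.6, 8.1.1, 12.1.1, 12.2 and 15 all describe Tier 2 as further people. Section 6.3.7 already gives Tier 1 completers a route to continued drug outside Tier 2. The footnote concerns repeat assessments and says nothing about counting, and its asterisk has no visible anchor in the table as extracted.

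Most of this stands. It shows what was intended, but it does not supply the missing sentence: nothing says that the four responders are cumulative or that Tier 1 subjects cannot fill Tier 2 places. The row that will be consulted at the decision says something else.

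A reader might infer more, namely that the rule is wrong and the 10%/10% rates fail, or that the footnote inflates type I error. The documents do not support this. The rates hold on the cumulative reading. On the printed label only the type II error fails, since type I error falls to 1.6%. Re-enrolment with each person counted once lowers type I error. It exceeds 10% only if responders are counted twice, which nothing in the plan prescribes. A reader might also see planned rollover in the 6 to 10 cycles of Section 7.9.2, since 4 + 6 = 10, but that section concerns treatment duration and does not mention re-enrolment.

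**Conclusion.** The point holds as a defect in how the decision rule is written. The design itself is sound.

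- The final row of Table 4, applied as printed, gives 71.3% power and 28.7% type II error, against a stated type II error below 10%. This needs no assumption beyond the label and the Tier 1 gate.
- The stated rates are correct (9.3% and 90.2%) for at least 4 of 37 distinct subjects, which is almost certainly the intended rule.
- The Tier 2 footnote contradicts the description of Tier 2 as 25 further subjects. With single counting its effect is small if only responders re-enrol: power 89.5% at worst, with type I error below 10%. The loss is larger if many Tier 1 subjects re-enrol regardless of response. The re-enrolment rates are assumptions.
- The figure of 23.4% for type I error belongs only to hypothetical double counting and should not be read as a property of this plan.

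The intended design clears its limits narrowly (9.3% and 9.8% against 10%), so there is little room for a loose count. The wording should be settled before Tier 1 results are used.

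**What to change.** 1. Relabel the last row of Table 4 as total responders among all 37 distinct subjects (Tier 1 + Tier 2), threshold unchanged at 4 or more.
2. Use the same wording in the text of 12.1.1 and in Section 15, and state there that each subject counts once.
3. Delete the footnote to the Tier 2 schedule in Section 6.1. Alternatively, reconcile it with the 25 further subjects and with Section 6.3.7 by stating that Tier 1 subjects who continue vactosertib are not among the 25 Tier 2 subjects and are counted by their Tier 1 result.
4. Bring the end-of-tier note on the Tier 1 schedule into line with its Tier 2 counterpart, so that it refers to continuing treatment and not to accrual.

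The cost is a few wording changes in one amendment. Sample size, gate, threshold and stated error rates all stay as they are.
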